2.3 Assessment of objectives

Assessment of primary endpoint

To assess the primary endpoint, research endoscopy findings (after the end of the follow-up period) will not be taken into account.

Because of the nature of the study, only participants who accepted the invitation to the Cytosponge™ test gave consent to the use of their data for study purposes. In order to collect primary endpoint data in consented Cytosponge™ patients, non-responders of the invitation and usual care participants, at least one of the following different data sources will be used:

- 1) **Automated coded search** for BEs, OGDs, EACs or upper gastrointestinal (GI) referrals: carried out on the GP electronic clinical records for all participants in all sites.
- 2) **Manual case-note review** of the GP clinical record for all participants identified by the coded search plus a number of other participants depending on the capacity of the sites: some practices will include all participants, some will include no additional participants and others will perform a manual review on a sample of participants chosen at random by the Trial statistician.
- 3) **National Health Service (NHS) number linkage** with hospital records for a limited number of sites, depending on the availability of relevant hospital information systems that routinely capture relevant diagnoses and geographical proximity of site in relation to its linked hospital.
Note: NHS number linkage will not be performed for all hospitals. For instance, in London, this step may be forgone because of the high population density and the consequent difficulty in determining the hospital catchment of sites.

Automated coded searches will be run by the study sites. The central study team does not provide the practices with the codes as different codes are in use in different practices. Following this step, the sites will fill in a spreadsheet prepared by the Trial team asking for the following information by sex and 10-year age range (50-59, 60-69, 70-79, 80-89, 90+): type of upper GI referrals and investigations; upper GI diagnoses during follow-up; treatment for BE. PLR sites will be asked to fill in two different spreadsheets, one for their usual care and one for their intervention patients. They will also indicate in the online database how many endoscopy referrals, BEs and adenocarcinomas (and the affected patients) they will have found in their records.

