3.2.2 Per-protocol population

The per-protocol analysis will exclude any patient who we know should not have been randomised had the inclusion and exclusion criteria been followed precisely (for example, a patient outside of the age range). It may not be possible to identify individuals who do not meet the eligibility criteria in terms of acid-suppression use (see below).

The per-protocol analysis will also exclude any study subjects in the PLR group randomised to one study arm but erroneously assigned to the other and any participants who moved away before receiving the invitation to the test.

The per-protocol analysis will be performed for the primary endpoint only.

Using the number of case-note reviews available in a practice as the denominator, we will calculate the proportion of patients in a practice that have less than 6 months' worth of acid-suppressant medication prescriptions in the year preceding baseline. This proportion will be used as a threshold in our sensitivity analyses. However, practices recruited at the late stages of the Trial may not perform any additional case-note reviews other than for patients picked up by the local coded search of their clinical information system due to time restrictions. In order to overcome these issues, we plan to perform three different sensitivity analyses:

Sensitivity analysis 1: Exclude the practices we know have more than 20% of patients with less than 6 months' worth of acid-suppressant medication prescriptions as well as those practices for which this information is unknown i.e. there has been fewer than 20 patients whose notes have been reviewed manually.

Sensitivity analysis 2: Exclude only the practices we know have more than 20% of patients with less than 6 months' worth of acid-suppressant medication prescriptions.

Sensitivity analysis 3: Only exclude individual patients known to have had less than 6 months' worth of acid-suppressant medication prescriptions at randomisation.

Sensitivity analyses will be performed for the primary endpoint only.

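### Sensitivity analyses 1 and 2 classify practices on a medication share that over-weights coded-search hits, and the 20-review minimum does not distinguish hits from random reviews.

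*SAP*

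**What the plan says.** SAP section 3.2.2 defines a practice-level share of patients with short acid-suppressant use: "Using the number of case-note reviews available in a practice as the denominator, we will calculate the proportion of patients in a practice" with under 6 months of prescriptions in the year before baseline. It concedes that late-recruited practices "may not perform any additional case-note reviews other than for patients picked up by the local coded search", and then says: "In order to overcome these issues, we plan to perform three different sensitivity analyses".

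- Analysis 1 drops practices above 20%, and also those where the share is unknown, which it defines as "there has been fewer than 20 patients whose notes have been reviewed manually".
- Analysis 2 reads: "Exclude only the practices we know have more than 20% of patients with less than 6 months' worth of acid-suppressant medication prescriptions". It does not repeat the minimum.
- Analysis 3 excludes individual patients and does not use the practice share.

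Section 2.3 determines whose notes are reviewed. Manual review is done "for all participants identified by the coded search plus a number of other participants depending on the capacity of the sites". Some sites review everyone, some nobody further, and some a random sample chosen by the trial statistician. The coded search looks "for BEs, OGDs, EACs or upper gastrointestinal (GI) referrals".

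**The concern.** The 20% rule is meant to describe the practice, but outside full-review practices the reviewed set is not a sample of the practice. Patients who were investigated or referred during follow-up are always in it; the rest are there only as site capacity allows. The same threshold therefore measures different things in different practices.

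The minimum of 20 tests how many notes were read, not how they were chosen. A practice with 20 hits and no random review counts as known, on a share that describes only its investigated patients.

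Section 7.1.1.3 presents these analyses as the control for short medication exposure. If practices are kept or removed on an unrepresentative share that depends partly on events after randomisation, agreement or disagreement with the main result is harder to read.

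**Working it through.** The SAP gives no operating figures for this rule, so there is nothing to reproduce. The check has three parts.

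**Inputs**
- Hit rate: not given. The 10% clinical endoscopy referral rate in section 2.5.2 (12 months, usual care) serves as a proxy. This is an assumption.
- Follow-up: 8 to 18 months (section 2.5.4). Scaled proportionally, the proxy runs from 10% × 8/12 = 6.7% to 10% × 18/12 = 15%.
- CLR practice size: strata from 50 to 225; projected mean 11,816/100 ≈ 118 (section 2.5.2).
- PLR practice size: not given. Section 2.5.5 lists 40 slots, later 10 more, of 250 patients each. That is list capacity. With 5390 PLR participants, 40 to 50 filled slots (an assumption) would average 5390/50 ≈ 108 to 5390/40 ≈ 135.

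**1. Weight of hits in a practice with a random sample.** Take 118 patients, a 10% hit rate and 20 random reviews of non-hits (the reading given by Table 1 in section 2.3).
- Hits: 118 × 0.10 = 11.8.
- Share of denominator: 11.8/(20 + 11.8) = 37%, against 10% of patients.
- If the short-use share is h among hits and r among others, the plan expects 0.37h + 0.63r, while the practice value is 0.10h + 0.90r. The error is 0.27(h − r).
- In a hits-only practice the error is h − (0.10h + 0.90r) = 0.90(h − r).

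The SAP gives neither h nor r, so the sign and size of h − r are unknown. If the two differed by 10 percentage points, the share would be off by 2.7 points in the first case and 9 points in the second.

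**2. Chance that a hits-only practice passes the minimum.** P(X ≥ 20), X ~ Binomial(practice size, hit rate):

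| Practice size | 6.7% (8 months) | 10% (12 months) | 15% (18 months) |
|---|---|---|---|
| 108 | <0.1% | 0.5% | 18% |
| 118 | <0.1% | 1.3% | 31% |
| 135 | <0.1% | 4.8% | 56% |
| 175 | 1.3% | 30% | 93% |
| 225 | 12% | 74% | about 100% |

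The 15% column does not fit the last-randomised practices: randomisation ended on 05/04/2019 and data lock was expected on 31 January 2020 (section 6.2), under 10 months later.

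**3. Analysis 2 without a minimum.** If known does not carry the 20-review definition there, a practice with 3 reviews is excluded as soon as one patient has short use. With a true share of 10% and representative reviews, that has probability 1 − 0.9³ = 27%.

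**The case against.** The plan acknowledges the gap. Practices with fewer than 20 reviews are dropped in analysis 1 for lack of information and, if the definition carries over, kept in analysis 2, so the two analyses bracket them. Analysis 3 and the individual-level comparison at the end of section 3.2.2 do not use the practice share. This stands, but the bracketing covers only practices below the count. A practice with 20 or more reviews, hits-only or mixed, is treated identically in both analyses.

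A reader might infer that late practices are generally kept or dropped on hits alone. The documents do not support that:
- The text says such practices "may not perform any additional case-note reviews other than for patients picked up by the local coded search", which is a possibility and not a rule.
- Most hits-only practices of ordinary size would fall below 20 reviews, as the table shows.
- Using 250 patients would give 88% at the 10% rate, but 250 is a list allowance and not an observed size.
- Ten per cent is not a floor for late practices, whose follow-up is shorter. Urgent referrals and endoscopies after a positive test could raise the rate, but the SAP gives no figure.

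A reader might also infer a bias between arms. Endoscopies after a positive test occur only in the intervention arm and can become hits, so whether a CLR practice counts as known could depend on its arm. But practices engaged later use individual randomisation (section 2.5.1), and excluding a PLR practice removes both arms together. Nor can a direction of bias be claimed: medication use is measured before baseline, and nothing in the SAP says how it differs between hits and other patients.

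**Conclusion.** The point holds in a limited form. As written, the practice share over-represents coded-search hits wherever review is not complete, and a larger practice can count as known without a single randomly chosen review. Analysis 2 leaves its definition of known unstated.

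The over-representation follows from the stated rule alone; its size (37% of the denominator against 10% of patients in the example) rests on the assumed 10% hit rate and 20 random reviews. Hits-only practices passing the minimum is a realistic prospect at 175 patients or more with about 12 months of follow-up, and unlikely at 135 or fewer unless follow-up is longer or the hit rate higher.

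The effect is confined to two sensitivity analyses of the primary endpoint. The direction of any bias is unknown, and arm imbalance is mainly a concern for CLR practices. It would go too far to call the two analyses uninterpretable; this is a cheap improvement to them.

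**What to change.** In section 3.2.2:

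1. Calculate the share from full-practice reviews where they exist, and otherwise from randomly selected reviews only. If hits are added, give them their weight in the practice (number of hits divided by practice size). Where the random sample is drawn only from patients the coded search did not identify, as Table 1 describes, this weighted version represents the whole practice.
2. Apply the minimum of 20 to full-practice or randomly selected reviews only.
3. Treat hits-only practices as unknown, whatever their number of hits.
4. State that the same definition applies in both analyses: unknown practices are excluded in analysis 1 and retained in analysis 2.

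The cost is a few sentences and a few lines of code. The trial statistician draws the random samples, so those reviews should be identifiable. The drawback is that more practices become unknown and leave analysis 1, which should be reported with the number excluded for each reason.

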	Negative	A randomly selected number of patients who have not been identified by the coded search will have their records reviewed, which will show a BE diagnosis.	A randomly selected number of patients who have not been identified by the coded search will have their records reviewed and no BE diagnoses will be found.
			N/A
			Most patients not identified by the coded search will not have their records reviewed manually.

The primary endpoint will be histological confirmed BE (column “BE diagnosis” in Table 1 plus any BEs picked up by the NHS number linkage exercise) only. (The case-note review should make clear where the BE was confirmed on histology or whether it was just the impression on endoscopic that was not confirmed.) Patients with BE identified via any of the three routes (automated search plus manual confirmation, manual search, record linkage) will be considered to have BE. Patients whose records have not been searched by any of the three approaches will be considered to have missing BE status. All other patients will be considered not to have a BE diagnosis. All patients with a BE/OGD/EAC/upper GI referral should have a manual review to confirm the diagnosis; if they have not had a manual review, their BE status will be considered as (partially) missing and handled through multiple imputations (of the outcome of the missing review).

Approximate balance in the number of full case-note reviews performed at random should be ensured between the two arms for practices in the CLR group.

Important! BEs known to the study team but not identified through at least one of the three methods describes above will not count towards the primary endpoint analysis. This is most likely to apply to cases detected following a positive Cytosponge™-TFF3 stain and resulting in an endoscopy performed by a study gastroenterologist. This rule is to ensure that the same data collection methods are used in the two study arms (as trial endoscopies are not available in the usual care arm) and helps avoid any biases. However, as a sensitivity analysis, all BEs known to the study team (prior to the exit research endoscopies) will be included. . For statistics relating only to the Cytosponge™ (e.g. PPV of the TFF3 stain), all cases of BE will be included.

Assessment of secondary endpoints

To be assessed using data from the intervention arm *only* (include all BE regardless of the route of study ascertainment):

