Further investigations on this will compare the proportion of BEs detected in patients with less than 6 months' worth of acid-suppressant medication prescriptions vs the proportion of BEs detected in patients with more than 6 months' worth of such prescriptions. Because of the nature of the data (aggregated data + individual-level data for consented Cytosponge™ patients and patients who have their case-note reviewed), this exercise will only be performed with the individual-level data available.

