5.3 Prior medications and treatments

Acid suppression medication data at baseline is available in aggregated form for all practices. Only medication dose and drug name (not length of treatment) will be available for all individuals.

A number of patients selected at random, both in the usual care and the intervention arm, will have their medication data at baseline reviewed and their medication data at end of study collected at the end of their follow-up period. A case-note review CRF will be filled in for each one of them. For these patients, length of treatment will be available in three monthly categories up to one year and more than one year.

Aggregated data on medication will be compared to medication data gathered during case-note reviews in those practices performing a review of all of their patients.

6. Interim analysis and timing for analysis

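### Sensitivity analysis 3 excludes on an exposure status known for nearly all BE cases but only some non-cases, so its arm-specific BE rates are too low, while the rate ratio is little affected

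*SAP*

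**What the plan says.** Section 3.2.2 plans three sensitivity analyses of the primary endpoint to deal with patients who had too little acid-suppressant exposure. Analyses 1 and 2 drop whole practices. Analysis 3 works on individuals and is to "Only exclude individual patients known to have had less than 6 months" of prescriptions at randomisation.

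Whether that is known depends on the data source:

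- Section 5.3: "Only medication dose and drug name (not length of treatment) will be available for all individuals". For patients with a case-note review, "For these patients, length of treatment will be available in three monthly categories up to one year" and as more than one year. Section 2.3 also lists length of acid-suppressant medication among the items recorded at manual review.
- Section 2.3, on who is reviewed: manual review is "of the GP clinical record for all participants identified by the coded search plus a number of other participants", the extra number depending on site capacity. Some practices review everyone, some review nobody extra, and some review a random sample.
- Section 2.3, on flagged patients: "All patients with a BE/OGD/EAC/upper GI referral should have a manual review to confirm the diagnosis".
- Table 1 in Section 2.3, on the rest: "Most patients not identified by the coded search will not have their records reviewed manually".
- Section 3.2.2, on practices recruited late: they "may not perform any additional case-note reviews other than for patients picked up by the local coded search".

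**The concern.** A BE case reaches the primary endpoint mostly by being flagged and then reviewed, and the same review reveals short exposure. A patient without BE is usually not flagged, and in many practices is not reviewed. Whether ineligibility is known therefore depends on the outcome. Under analysis 3 a short-exposure case is removed, while a short-exposure non-case usually stays and contributes person-years.

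The analysis is meant to show the result in patients who met the exposure criterion. As written, its numerator is close to that population and its denominator is not. The SAP reports BE rates per 1000 person-years by arm as well as the rate ratio, so the depressed rates would appear in the output. If exposure were better known in one arm, the ratio would move too.

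**Working it through.** **The plan's own figures.** The SAP gives no figure for analysis 3, so I start from the planning rates in Section 2.5.2.

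- Intervention: 0.27 × [0.04 × 0.85 + 0.15 × 0.1 × 0.06] + 0.73 × 0.1 × 0.06 = 1.3803%.
- Usual care: 0.1 × 0.06 = 0.6%. The ratio is 2.3005.
- The sample size for 90% power at two-sided 5% reproduces as 6764 with the unrounded 1.3803% (6768 with 1.38%), which is 3382 per arm.

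**Assumed inputs (not in the SAP).**

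- q, the share of patients with short exposure: 5-30%. The 20% in Section 3.2.2 is a threshold for dropping a practice, not an expected share.
- f, the share of non-cases reviewed: 10-50%. The lower end follows from Section 2.5.2: if 10% are referred and 6% of those have BE, then 0.10 × 0.94 / 0.994 = 9.5% of non-cases are flagged and should be reviewed anyway.
- All BE cases are reviewed, the BE rate does not depend on exposure, and each patient contributes one year.

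**Formula.** With C cases and NC non-cases in an arm:

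rate in analysis 3 = C(1 − q) / [C(1 − q) + NC(1 − qf)].

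If every short-exposure patient could be removed (f = 1), this returns the planning rate. For a rare outcome the ratio of the two is close to (1 − q)/(1 − qf).

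**Example, q = 20%, f = 10%.**

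- Usual care: C = 20.29, NC = 3361.7. Rate = 16.23 / (16.23 + 3294.5) = 0.490%, a factor of 0.817.
- Intervention: C = 46.68, NC = 3335.3. Rate = 37.35 / (37.35 + 3268.6) = 1.130%, a factor of 0.818.
- Ratio: 2.304 against 2.3005.

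**Factor on the arm rate** (usual care; the intervention arm agrees within 0.002):

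| q | f = 10% | f = 25% | f = 50% |
|---|---|---|---|
| 5% | 0.955 | 0.962 | 0.975 |
| 10% | 0.910 | 0.924 | 0.948 |
| 20% | 0.817 | 0.843 | 0.889 |
| 30% | 0.723 | 0.758 | 0.824 |

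Across this table the rate ratio stays between 2.301 and 2.306. If short-exposure patients had half the BE rate, the factor against the true long-exposure rate would still be 0.82 at q = 20%, f = 10%.

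**Unequal coverage.** Suppose exposure is also known for everyone who takes the test, with f = 10% otherwise. Intervention coverage becomes u + (1 − u) × 0.10, where u is uptake: 31.6% at u = 24% (Section 2.5.3) and 34.3% at u = 27% (Section 2.5.2). Usual care stays at 10%.

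| q | Ratio at 24% uptake | Ratio at 27% uptake |
|---|---|---|
| 10% | 2.353 (+2.3%) | 2.359 (+2.6%) |
| 20% | 2.409 (+4.7%) | 2.423 (+5.3%) |
| 30% | 2.469 (+7.3%) | 2.491 (+8.3%) |

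All shifts are away from the null.

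**The case against.** **The tested quantity is the ratio.** This largely stands. With equal coverage the deflation cancels almost completely. A reader might infer that the treatment effect in analysis 3 is off by as much as the rates are, but the documents do not support that.

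**The ratio shift is conditional and small.** This also stands. Section 3.2.2 names "individual-level data for consented Cytosponge™ patients and patients who have their case-note reviewed" as its individual-level sources, and Section 7.1.2 plans PPVs by duration of prescriptions. However, Section 5 lists only medication and dose on the Baseline Clinical CRF, so it is unclear whether prescription length is known for attenders. Confirmatory endoscopies in test-positive patients without BE would add some intervention-arm reviews. Those patients are a subset of attenders, so the effect is smaller than in the attender scenario. At planning values (about 47 and 20 events) the standard error of the log ratio is √(1/47 + 1/20) = 0.27, so a 4.7% shift is about 0.17 standard errors.

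**The deflation may be modest.** This stands in part. A reader might infer rates nearly 30% too low, but that needs about 30% ineligible, which has no source in the SAP, and almost no non-cases reviewed. Participants were selected by automated search and manual record review (Section 3.4), some practices review everyone, and flagged non-cases are reviewed.

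**The limitation is acknowledged.** Only partly. Section 3.2.2 says some ineligible patients cannot be identified and that late practices may lack extra reviews. It does not say that identification follows the outcome. Analyses 1 and 2 remove cases and non-cases together, so they do not share this mismatch.

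**Not every case will be reviewed.** True. Section 2.3 says should, with imputation otherwise, and cases found only by NHS linkage are checked with sites without a stated exposure record. Hence nearly all cases, not all.

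**Conclusion.** The exclusion in analysis 3 depends on the outcome, and its arm-specific BE rates will be below those of patients with adequate exposure wherever review is incomplete. The size is about 5-18% if 10-20% are ineligible and 10-50% of non-cases are reviewed, and under 5% if only 5% are ineligible. Both inputs are assumptions. The direction needs only that exposure is known more often for cases than for non-cases.

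The rate ratio is almost unaffected when review coverage is equal across arms. If exposure is also known for attenders, it moves away from the null by about 2-5% at 24% uptake (10-20% ineligible) and 3-8% at 27% (10-30% ineligible).

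The primary result and analyses 1 and 2 are untouched. This is a wording change worth making to one sensitivity analysis and does not threaten the trial's conclusion.

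**What to change.** Reword analysis 3 so that the exclusion applies only where exposure is ascertained independently of outcome, with case-note review as the source in both arms:

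- **Practices that reviewed all records:** use them as they are.
- **Practices with a random review sample:** keep eligible cases in the numerator and multiply the practice-arm person-years by the eligible proportion among its randomly reviewed patients. If the sample was drawn only from unflagged patients, as Table 1 suggests, scale only the unflagged person-years and use the known status of flagged patients.
- **Practices with no random reviews:** either omit them or apply the pooled proportion from random reviews in the same randomisation group (CLR or PLR). State which in advance.

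If the present rule is also reported, interpret its rate ratio and not its arm rates.

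The cost is a wider interval in this one analysis. Omitting practices without random reviews could be expensive: later practices were individually randomised (Section 2.5.1), and the PLR group carries 5390 of 5390 + 2120 = 7510 equivalent patients, about 72% (Section 2.5.2). The pooled proportion keeps them, but assumes that their eligible share resembles that of the reviewed practices.

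### The exploratory comparison of Barrett's oesophagus (BE) detected by prescription length uses a sample partly selected on referral, diagnosis or testing, with no weighting or separation by source or arm, so its proportions are inflated and its ratio may be biased

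*SAP*

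**What the plan says.** The last paragraph of SAP section 3.2.2 adds a further investigation to the per-protocol sensitivity analyses. The stated aim is to "compare the proportion of BEs detected in patients with less than 6 months' worth of acid-suppressant medication prescriptions vs the proportion of BEs detected", the second group being those above that length. The data are "individual-level data for consented Cytosponge™ patients and patients who have their case-note reviewed", and "this exercise will only be performed with the individual-level data available".

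Section 2.3 settles who has a case-note review. It is done "for all participants identified by the coded search plus a number of other participants depending on the capacity of the sites", and the extent varies: "some practices will include all participants, some will include no additional participants", while others review a random sample. Table 1 in the same section adds: "Most patients not identified by the coded search will not have their records reviewed manually". Section 3.2.2 says that practices recruited late "may not perform any additional case-note reviews other than for patients picked up by the local coded search".

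The SAP sets no weights, no stratification by source or arm, and no restriction to random reviews for this comparison. Section 5.3 gives length of treatment only for patients with a case-note review.

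**The concern.** A patient enters this comparison by being flagged for BE, endoscopy, cancer or an upper GI referral, by taking the Cytosponge test, or by being drawn for an additional review. The first two routes are tied to how BE comes to be detected. The third depends on site capacity. A crude proportion over such a sample does not estimate the proportion of BE detected in the trial population. A crude contrast between prescription groups can be distorted if the groups enter by these routes at different rates.

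The comparison bears on whether patients below the 6-month criterion changed BE detection, and it would be read beside sensitivity analyses 1 to 3. Correcting those three would not correct this one.

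**Working it through.** **Inputs (SAP section 2.5.2).** Referral to endoscopy in usual care p = 10%; BE in those referred 6%; BE prevalence 4%; Cytosponge sensitivity 85%; uptake u = 27%. Practice size is 11,816/100, about 118. Assumed: coded-search hits are about the 10% referred, arms are 1:1, and f is the fraction of the remaining patients given an additional review. The SAP gives no overall value for f, so it is ranged.

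**The plan's own figures reproduce.** Usual care: 0.10 × 0.06 = 0.60%. Intervention: 0.27 × (0.04 × 0.85 + 0.15 × 0.006) + 0.73 × 0.006 = 1.3803%. A two-sided 5% test with 90% power on these rates needs 3382 per arm, 6764 in total, as stated.

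**Level of the proportions.** Share of the arm in the sample:
- usual care: n_U = p + f(1 − p)
- intervention: n_I = u + (1 − u)n_U

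The crude proportions are 0.006/n_U, 0.013803/n_I and, pooled, (0.006 + 0.013803)/(n_U + n_I). The full-cohort pooled value is 0.019803/2 = 0.99%. At f = 0 the pooled figure is 0.019803/(0.10 + 0.343) = 4.5%.

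| f | Usual care | Intervention | All sources, both arms |
|---|---|---|---|
| 0 | 6.0% (10.0×) | 4.0% (2.9×) | 4.5% (4.5×) |
| 10% | 3.2% (5.3×) | 3.4% (2.5×) | 3.3% (3.3×) |
| 30% | 1.6% (2.7×) | 2.6% (1.9×) | 2.2% (2.2×) |
| 100% | 0.60% (1.0×) | 1.38% (1.0×) | 0.99% (1.0×) |

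The usual-care extreme is 1/p, so it runs from 11.1 to 9.1 as p goes from 9% to 11%. In a usual-care practice of 118 with 20 random reviews, the proportion is 0.708/31.8 = 2.2%.

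**Ratio between prescription groups (short over long).** All group-specific referral shares below are assumptions.
- No difference in referral, uptake or review fraction: both groups inflate equally. A true ratio of 2.0 stays 2.0 at every f.
- Referral 6% (short) against 11% (long), equal true detection, hits only, no takers: 0.11/0.06 = 1.83 where the truth is 1.0. With takers at 27% uptake in both groups, short contributes 0.06 + 0.27 + 0.73 × 0.06 = 0.3738 and long 0.11 + 0.27 + 0.73 × 0.11 = 0.4603, so the ratio is 1.23.
- Referral 15% against 8.75%, same set-up: 0.58 without takers, 0.421/0.530 = 0.80 with them.
- With 20 random reviews per practice, the first case gives 1.17 without takers and 1.10 with them; the second gives 0.84 and 0.89.
- Review fraction alone: take two equal-sized usual-care practices, both with 10% referral and 0.6% detection in each prescription group. One reviews hits only and has 30% short-prescription patients; the other reviews everyone and has 10%. Short: 0.006 × 0.4/(0.3 × 0.1 + 0.1) = 1.85%. Long: 0.006 × 1.6/(0.7 × 0.1 + 0.9) = 0.99%. The ratio is 1.87 where the truth is 1.0. Swapping the shares gives 0.64.

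**After weighting.** Inverse-sampling weights, or f = 1, return 0.60%, 1.38% and 0.99%.

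**The case against.** Section 3.2.2 does not say that the sources form one sample or that crude proportions are taken across arms. That is correct: pooling is the natural reading of the paragraph, but it is an inference.

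A reader might infer a tenfold inflation of the whole comparison. The SAP's inputs do not support that. Ten applies to usual-care patients in hits-only practices; with takers included, the pooled maximum is about 4.5. Section 2.5.2 also states its 10% after excluding urgent referrals, so if the coded search flags those too, the hit share is larger and the inflation smaller. In the other direction, 4.5 assumes that every taker can be classified by prescription length. Section 5.3 gives length only for reviewed patients and section 5 lists medication and dose for takers, yet section 7.1.2 plans predictive values by duration of prescriptions. If unreviewed takers dropped out, the hits-only sample over both arms would be inflated about 8.8 to 9.6 times, assuming that positive takers become hits and that the positive predictive value lies between 30% and 100%.

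A reader might also infer that the contrast reflects referral or testing instead of BE risk. The SAP does not show this. It gives no referral, uptake or review figures by prescription length, and the ratio is unbiased if none differs. The stated outcome is BE detected, which depends on referral and testing even with complete review. For example, with assumed uptake of 30% (long) against 15% (short) and equal prevalence, the full cohort itself gives a long-over-short ratio of 1.27. What selection adds is the shift from 1.27 to 0.90 at f = 0.

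Finally, the analysis is labelled as further investigation, has no decision rule, does not feed the primary result, and discloses its restriction to individual-level data. All of that stands and limits the weight of the point. Disclosing the restriction does not deal with the selection.

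**Conclusion.** The point holds for an exploratory analysis. As written, the comparison rests on a sample partly selected on referral, diagnosis or testing, with review fractions that vary from none to all by practice and no weighting or separation planned. Its proportions will overstate BE detection unless review is complete: by up to about 4.5 times if all three sources are pooled, and up to 10 times for usual-care patients in hits-only practices. These sizes rest on the section 2.5.2 inputs and on equating hits with the 10% referred.

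The ratio may be biased in either direction. In the assumed 6% against 11% case it is 1.83 without takers and 1.23 with them, where the truth is 1.0. That bias is conditional on referral, uptake or practice review fraction differing by prescription length, which the SAP neither states nor excludes. The primary endpoint result is not affected.

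**What to change.** Replace the last sentence of SAP section 3.2.2 with a rule along these lines:

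- Make the comparison in practices that reviewed all their patients and in practices that made random additional reviews. In the latter, weight unflagged reviewed patients by the inverse of the practice's sampling fraction. Leave out hits-only practices.
- Report by arm, with Cytosponge takers separate from other patients.
- Include takers only where prescription length is recorded, and state the source of that information for takers without a case-note review, so that sections 5, 5.3 and 7.1.2 agree.
- Describe the result as exploratory and as BE detected, not BE risk.

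The cost is a change of wording and a simple weighting step. The price in precision is real: fewer practices, probably losing mainly the late-recruited ones, and wider intervals around an outcome expected in about 1% of patients.
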